3.4.2.2 Stage II

Given the nature of the study (pilot) and associated small sample size, descriptive statistics will be calculated, but no group comparisons will be completed.

Primary Outcome 2.1 (Comprehension & Recall): The Personal Information and Meaning of Information accuracy scores will be totaled for all participants. Mean, median, and standard deviation will be calculated. Exploratory analyses will evaluate trends in whether specific types of feedback information (e.g., neuroimaging vs. amyloid/tau burden) were better understood than others, and whether group differences exist (i.e., participants vs. co-participants, by race, by cognitive status).

Primary Outcome 2.2 (Psychological Reactions): Mean, median, and standard deviation of total scores on the GDS-15, BAI, and IES will be calculated. Change in total scores on the BAI and GDS-15 will be calculated by comparing Stage II scores with Stage I screening scores. Descriptive statistics will also be calculated for these change scores.

Secondary Outcome 2.3 (Satisfaction): Answers to the qualitative questions will be reviewed individually for suggestions and themes.

SECTION 4: MONITORING

4.1 Risk Monitoring

4.1.1 Stage I

It is not expected that discussing DAT risk disclosure preferences or needs will cause significant distress or exacerbation of mood symptoms; however, all participants in the Year 1 Needs Assessment will complete a brief measure of mood and anxiety, including the Geriatric Depression Scale – 15 Item version (GDS-15)¹ and the Beck Anxiety Inventory (BAI)² following participation in the semi-structured interview. A study team member will also be present in the room, or available virtually with the participant or co-participant for the entirety of the session to monitor distress. Each of the measures have empirically supported cut-off scores for determining clinically significant depression, anxiety, and event-related distress; individuals who endorse clinically significant depression or anxiety on the GDS-15 or BAI at the end of the session, or who appeared distressed during the session, will undergo a risk assessment and follow-up (see below). The study safety plan to determine need for risk assessment or intervention is included in Appendix A. Of note, for video or phone sessions, at the start of each session, the participant/co-participant will be asked to provide a call-back number in case he/she is disconnected from the technology, as well as current location; this information will not be stored in the participant's/co-participant's file, but will be used as a reference in case of emergency or safety issue.

4.1.2 Stage II

It is possible that patient and informant participants may experience psychological distress as a result of hearing feedback about their current cognitive status and risk for developing DAT, particularly if the feedback indicates elevated risk. Although DAT risk disclosure has been found to be generally safe and well-tolerated in the literature^{3,4}, we will conduct careful screening of mood, anxiety, and event-related distress utilizing psychometrically sound evaluations. Specifically, each participant and co-participant will repeat the GDS-15 and BAI, and complete the Impact of Event Scale (IES)⁵ at the Year 2 disclosure session as well as at 1- and 6-week follow-up. Any clinically significant elevation of scores on the GDS-15 or BAI, a score of 24 or higher on the IES, and/or other indication of new or exacerbated mood symptoms will result in a more advanced evaluation during the feedback and follow-up sessions (see Appendix A). In addition, participants and co-participants will be given contact information for the study team and encouraged to call ARF or ML with any concerns or needs related to their reactions to the disclosure session.

4.2 Safety Assessment: In the case of safety concerns in either Stage, a risk assessment and follow-up will be conducted. A licensed psychologist (*ARF*, *BMH*, or *JSR*), who will be available during all sessions either in-person or virtually, will evaluate the patient's or informant's severity of psychological symptoms and risk of self-harm. The clinician will take additional action as needed to either provide immediate transfer to emergency care (in the case of active threat), or facilitation of clinical care or supportive resources, per participant request

(in the absence of active threat). All participants will also be provided with emergency contact cards with local, 24/7 resources if emergent mood issues arise between sessions. A summary of the project suicide safety plan is included in Appendix A.

4.3 Adverse Events Reporting: Participant mood and distress will be carefully assessed for the 50 Year I dyads using the Geriatric Depression Scale – 15 Item version (GDS-5) and the Beck Anxiety Inventory (BAI). These measures, in addition to the Impact of Event Scale (IES), will be administered to the patient and informant dyads receiving pilot feedback in Year 2 to determine (a) whether changes in mood or distress occur, and (b) whether these changes are attributed to study participation. The GDS and BAI have empirically supported cut-off scores for determining clinically significant depression, anxiety; scores will therefore be used to define the nature of any events (unanticipated vs. anticipated, adverse vs. serious adverse) and relationship of these events to study participation (related vs. unrelated). The IES does not have a validated cutoff; however, we will treat a score of 24 or higher as warranting additional study team follow-up.

Information regarding non-serious adverse events (i.e., an elevation in mood or anxiety symptoms as a result of study participation) will be reported directly to the PI, who will compile and submit a report to independent Safety Officer (SO). The SO for this project is [name] ([contact]). Similarly, serious adverse events that are determined to be unrelated to study participation will be reported to the PI, recorded in a secure study database, and reported to the SO. These summary reports will be submitted to the SO on a quarterly basis.

Unanticipated adverse events or serious adverse events deemed related to study participation (i.e., acute exacerbation or onset of severe depression or anxiety, hospitalization for emotional reasons, and/or preparation for or engagement in self-injurious behavior as a result of risk disclosure results) will be reported immediately to the study PI. Consistent with Office of Human Research Protection, Institutional Review Board guidelines for the study's parent institution, and NIA standards, serious study-related adverse events resulting in life-threatening outcome or death will be reported to the SO and NIA program officer as soon as possible, and within 24 hours of study PI knowledge of the event. Other serious study-related adverse events and unanticipated adverse events will be reported as soon as possible, and within 48 hours of study PI knowledge of the event. The PI, in conjunction with the SO, will review the case and relevant study data to determine whether the study should be halted or how it may be altered to promote safety.

Additionally, the SO will meet at least twice per year via telephone or video conferencing to review adverse events and their outcomes, and to generate recommendations for study protocol alteration for improved safety (or termination of the study, if deemed necessary).

SECTION 5: ETHICS AND DISSEMINATION

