Primary Outcomes:	
Stage I:
 
 (a) Interest in different levels of risk disclosure feedback (b) Preferences for different levels of risk disclosure feedback (c) Perceived personal threat of DAT (d) Perceived benefits of/rationale for risk disclosure (e) Perceived barriers to risk disclosure (f) Importance of risk disclosure feedback elements 
Stage II:
 
 (a) Comprehension/recall of personal risk information (b) Psychological distress (mood, anxiety, and event-specific distress) (c) Satisfaction with feedback process (exploratory)

SECTION 1: Roles & Responsibilities - Contributorship

[name]. (ARF) – Principal Investigator

Affiliations: University of Michigan, Department of Psychiatry

Contact: [contact]

Roles & Responsibilities:

Design conception and initiation
Preparation of protocol and revisions
Managing correspondence with clinical trials office
Publication of study reports
Preparation of manuscripts
Recruitment and screening of patients
Data collection
Data entry, verification
Statistical Analyses
Regulatory and compliance management/adverse event reporting

[name]., ABPP-CN (BMH) – Co-Investigator

Affiliations: VA Ann Arbor Healthcare Systems, Mental Health Service

University of Michigan, Department of Psychiatry

Contact: [contact]

Roles & Responsibilities:

Design conception and initiation
Mentorship

J. [name]. (JSR) – Co-Investigator

Affiliations: University of Michigan, School of Public Health

Contact: [contact]

Roles & Responsibilities:

Design conception and initiation
Mentorship

[name], B.S. (ML) – Research Associate

Affiliations: University of Michigan, Department of Psychiatry

Contact: [contact]

Roles & Responsibilities:

Preparation of protocol and revisions
Managing correspondence with clinical trials office
Preparation of study reports
Preparation of manuscripts
Recruitment and screening of patients
Data collection
Data entry, verification
Statistical Analyses
Regulatory and compliance management/adverse event reporting

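### Section 4.3 builds attribution into the definition of a non-serious adverse event, so elevations judged unrelated have no stated route to the Safety Officer

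*Combined protocol and SAP*

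**What the plan says.** Section 4.3 (Adverse Events Reporting) sets these routes to the Safety Officer:

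- Non-serious events: "non-serious adverse events (i.e., an elevation in mood or anxiety symptoms as a result of study participation) will be reported directly to the PI". The PI then compiles a report for the officer.
- Serious events judged unrelated: "serious adverse events that are determined to be unrelated to study participation will be reported to the PI, recorded in a secure study database", and then passed to the officer. For this stream and the one above, "These summary reports will be submitted to the SO on a quarterly basis".
- Serious events judged related: "serious study-related adverse events resulting in life-threatening outcome or death will be reported to the SO and NIA program officer as soon as possible", with a limit of 24 hours once the PI is aware. For the rest, the rule is: "Other serious study-related adverse events and unanticipated adverse events will be reported as soon as possible, and within 48 hours of study PI knowledge".
- Event-specific distress: the scale has no validated cut-off, but "we will treat a score of 24 or higher as warranting additional study team follow-up".

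The same section says that GDS and BAI scores will be used to classify events, including as related or unrelated. It gives no criteria for causality and names no assessor.

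Elsewhere, Section 2.3 makes Stage II a single-group study of 10 dyads, assessed right after disclosure and at 1 and 6 weeks. The summary table lists psychological distress as a Stage II primary outcome with three parts: mood, anxiety and event-specific distress. Section 4.1.2 foresees distress after feedback. It sends GDS-15 or BAI elevations, IES scores of 24 or more and other new symptoms to fuller evaluation, with no condition on cause.

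**The concern.** The wording that defines a non-serious event is introduced by *i.e.*, so it reads as a definition and not as an example. Someone must decide that a mood or anxiety rise was caused by the study before it becomes an event to compile. Serious events judged unrelated have an explicit route; non-serious elevations judged unrelated have none.

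That decision has little to rest on. There is no control group. A GDS or BAI score shows that symptoms rose, not why. The section on roles gives the PI design conception, data collection, statistical analysis and adverse event reporting. The Safety Officer is the only safety reviewer the plan calls independent, and nothing describes the officer checking attribution before a report is made. The officer may recommend changing or ending the study, and would do so on a record already sorted by the study team's view of cause.

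**Working it through.** The plan gives no figure on this point to reproduce. The check is to follow each kind of post-disclosure finding through Sections 4.1.2 and 4.3.

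| Finding | Judged related | Judged unrelated |
|---|---|---|
| Non-serious GDS-15 or BAI elevation | PI, then officer, quarterly | No route stated |
| IES of 24 or more, no mood or anxiety elevation | Evaluation and team follow-up; not named as an event | Same |
| Serious, fatal or life-threatening | 24 hours from PI knowledge | Quarterly; perhaps 48 hours if unanticipated |
| Other serious | 48 hours from PI knowledge | Quarterly; perhaps 48 hours if unanticipated |

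The top right cell and the IES row are the gaps in content. The last two cells of the right-hand column are the overlap in timing. Because Section 4.1.2 foresees distress, the unanticipated-event route may not catch the outcome under study.

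**Timing.** One quarter is 365.25 / 4 = 91.3 days, the longest wait for a quarterly report. If the wait is uniform over the quarter (an assumption), its mean is 91.3 / 2 = 45.7 days. Each person's follow-up is 6 × 7 = 42 days. For an event known on the day of disclosure and reported quarterly, the chance that the report comes after that person's 6-week visit is 1 − 42/91.3 = 0.54. For one known at week 1 it is 1 − 35/91.3 = 0.62.

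**What filtering could do, under assumed rates.** The documents give neither the rate of elevations nor the share judged unrelated. Let r be the proportion of the 20 people with an elevation and u the share judged unrelated and, on the strict reading, not listed. The officer expects 20r(1 − u) events and sees at least one with probability 1 − (1 − r(1 − u))^20, treating people as independent. Members of a dyad hear the same result, so independence is a simplification. Each cell gives the expected number and that probability.

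| r | u = 0 | u = 0.25 | u = 0.50 | u = 0.75 |
|---|---|---|---|---|
| 0.05 | 1.0; 0.64 | 0.75; 0.53 | 0.5; 0.40 | 0.25; 0.22 |
| 0.10 | 2.0; 0.88 | 1.5; 0.79 | 1.0; 0.64 | 0.5; 0.40 |
| 0.20 | 4.0; 0.99 | 3.0; 0.96 | 2.0; 0.88 | 1.0; 0.64 |

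The table shows only that, with 20 people, removing a few events matters. The finding does not depend on it.

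**The case against.** Several points on the other side stand, and they limit the claim.

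- *Silence is not prohibition.* Section 4.3 speaks of classifying any events as related or unrelated, which implies that unrelated ones are recorded. A reader might infer that such elevations never reach the officer. The text supports only that no route is stated.
- *The 48-hour rule for unanticipated events.* The sentence that sets it does not limit it to related events. A death during a study of remote feedback sessions could well be unanticipated. So it does not follow that timing turns on attribution alone; the rules overlap and the text does not say which prevails.
- *The clock.* The 24 and 48 hours run from the PI's knowledge, not from the event. With scheduled contacts at 1 and 6 weeks, an event between visits may be learned of late under any rule.
- *The IES.* A score of 24 or more leads to evaluation, and mood symptoms found there could meet the definition. The scale is anchored to receiving feedback, so distress on it is hard to call unrelated. What remains is that the score itself is not named as reportable.
- *The analysis.* Section 3.4.2.2 plans descriptive summaries of all GDS-15, BAI and IES scores and no adverse-event count, so no planned estimate is biased.
- *The officer's role.* The officer meets at least twice a year to review adverse events, and the PI reviews cases jointly with the officer. But the meetings review what has been reported as an event, and the joint review is described alongside the expedited reports. Neither is a stated check on attribution beforehand.

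Section 4.3 also says that its reporting follows outside standards, which cannot be checked from the documents. Expediting every serious event whatever its attribution would be a stricter policy on which reasonable people differ, not the correction of an error.

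**Conclusion.** The point holds as a gap in independent oversight during Stage II. As written, non-serious elevations judged unrelated have no stated route to the Safety Officer, and an IES score of 24 or more is not named as an event, in a single-group study where distress is a primary outcome. Serious events judged unrelated are delayed, not withheld: up to about 91 days, against 24 or 48 hours from PI knowledge, unless the rule for unanticipated events applies.

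The conclusion rests on reading the parenthesis in Section 4.3 as a definition. It does not extend to individual safety response or to the final dataset, and nothing suggests an intention to withhold events. The change is worth making because it is cheap and bears on the harm the study sets out to measure.

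**What to change.** In Section 4.3:

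1. Define the non-serious event without causality, as any new post-disclosure crossing of a trigger the plan already uses: GDS-15, BAI, or an IES score of 24 or higher.
2. List every crossing in the existing Safety Officer reports, with the pre-disclosure GDS-15 or BAI score where one exists and the team's attribution in a separate column. The IES, being anchored to the feedback, has no pre-disclosure score.
3. Reconcile the quarterly rule for unrelated serious events with the 48-hour rule for unanticipated events, so that it is clear which applies to a serious event during Stage II follow-up.
4. Let the officer record an independent view of relatedness.

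No threshold or clinical response changes. Section 3.3.2 excludes anyone above the GDS-15 or BAI cut-offs at Stage II screening, so, if the same cut-offs apply throughout, a later crossing is new by construction. The listing draws on at most 20 people × 3 assessments = 60 person-assessments, with scores already collected, and could be built from existing data if Stage II is complete. The cost is protocol wording, a short extra listing and a slightly less favourable event count.

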5.1 Research Ethics Approval & Protocol Amendments

All procedures detailed above fall within the parameters approved by the University of Michigan institutional review board. Any changes to these parameters or procedures will be proposed to and approved by the IRB through formal amendments prior to implementation.

5.2 Consent or Assent

All consent forms and others requiring authorized signatures will be approved by the University of Michigan IRB. A study team member will review the consent form for the specific Stage. The team member will pause after each section to solicit and answer questions. Comprehension of the procedures, risks, benefits, and other aspects of the study will be checked using a decision-making tool (a brief measure asking the participant to use his or her own words to review the contents of each section of the consent form before signing). These procedures will be followed regardless of whether the consent is completed in person or remotely via electronic consent.

5.3 Confidentiality

Information gathered from individuals contacted for initial screening is entered into a recruitment database file that is stored in the shared drive (accessible only to approved lab personnel) and password protected. This

centralized file will contain only the necessary information for contacting and determining eligibility and interest in the study, as well as assigned ID numbers for enrolled participants. For information regarding security and confidentiality of data from enrolled participants, see '[Data Management & Entry](#)'.

Participants will be made aware prior to enrollment in Stage I that they will not receive feedback regarding their risk for DAT as part of the Stage I study. As mentioned above, a copy of the consent form is uploaded into the participant's University of Michigan electronic medical record as a 'Research Document' to communicate current research participation to medical providers.

5.4 Declaration of Interests

None of the study investigators have any financial or competing interests to declare.

5.5 Access to Data

Study data will remain housed within the [name] laboratory at the University of Michigan and will only be available to authorized study team members or members of oversight committees (e.g., IRB).

5.6 Ancillary and Post-Trial Care

As noted above, there are procedures in place to alert the principal investigator and take any needed action to deal with serious adverse events or harms that occur during the study session. As stated in the consent form, participants are instructed to seek immediate medical attention for any serious adverse events that arise after the study session, rather than waiting to contact or hear back from study personnel. Participants are instructed that any medical appointments that are attended after the study will be billed through the patient's regular insurance avenues.

As this study is examining a non-clinical sample of healthy older adults, and DAT biomarker risk evaluation is not considered part of the standard of care for older adults, there is no obligation to provide a waitlist control or delayed access to treatment to individuals assigned to the sham condition.

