2.1 Comprehension and recall of personal risk disclosure information

2.2 Psychological reactions to personal risk disclosure information

2.3 Satisfaction with the feedback process (exploratory)

SECTION 2.3: Trial Design

The Stage I Needs Assessment is an observational study with no intervention or randomization. Stage II will involve a clinical trial, with the risk disclosure feedback serving as the behavioral intervention. The study will use a single-group design. All 10 participant-co-participant dyads (5 Non-Hispanic African-American, 5 Non-Hispanic White) will receive feedback about the participant's DAT risk. Outcomes will be measured immediately following feedback and at 1- and 6-weeks following risk disclosure. For more information regarding design, see *Methods* section.

SECTION 3: METHODS

SECTION 3.1 Participants: Inclusion & Exclusion Criteria

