Comprehension and recall of personal risk disclosure information will be measured as accuracy scores on a series questions about the patient's results and the meaning of different messages provided during feedback in regards to AD/DAT risk (i.e., "My Attention was [Normal/Impaired/Don't Know]"). The questionnaire will result in two scores: a Personal Information score and a Meaning of Information score (as it is possible that an individual may accurately remember his/her own information, but misinterpret it, or may understand the meaning of risk information, but incorrectly recall his/her own feedback).

Psychological reactions to personal risk disclosure information will be measured both in terms of general mood and anxiety, as well as feedback-specific distress.

Depression: Mood will be assessed using the self-administered Geriatric Depression Scale – Short Form (GDS-15)³²⁻³³. The GDS-15, a 15-item assessment of depressive symptoms, has been adapted to remove common depression symptoms often conflated with normal aging (i.e.,

somatic symptoms). It asks the participant to rate the presence of mood symptoms over the past two weeks.

Anxiety: The BAI³⁴, also validated for use with older adults³⁵ is a 21-item measure of the perceived severity ('not at all' to 'severely') at which the participant is experiencing anxiety symptoms over the past week.

Feedback-Specific Distress: We will utilize a revised version of the Impact of Genetic Testing for Alzheimer's Disease (IGT-AD) Scale, which itself is based on The Impact of Event Scale (IES)³⁶. The scale will be specifically anchored to the 'life event' of receiving feedback; responses will be slightly modified to assess the impact of receiving any and all AD indicator results (not solely genetic information). The IES and IGT-AD have been utilized to measure test-related distress in previous risk disclosure studies³⁷⁻³⁹, including REVEAL. Participants who have a negative score of 24 or more will be contacted by PI for follow-up with participant/co-participant.

Exploratory Outcomes

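### Stage II schedules no question about care, hospitalization or self-harm since the last contact, and days 7 to 28 after disclosure fall outside both GDS-15 and BAI recall

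*Combined protocol and SAP*

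**What the plan says.** **Timing.** Section 2.3 states: "Outcomes will be measured immediately following feedback and at 1- and 6-weeks following risk disclosure". Section 4.1.2 gives the GDS-15, BAI and IES at all three contacts.

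**Recall periods.** Under Primary Outcomes in Section 3.3.2, the GDS-15 asks the person to "rate the presence of mood symptoms over the past two weeks", and the BAI grades how severely the person is "experiencing anxiety symptoms over the past week". The impact scale is tied to the event of receiving feedback, with no recall period given.

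**Use for safety.** In Section 4.3 these measures "will be administered to the patient and informant dyads receiving pilot feedback in Year 2 to determine" whether mood or distress has changed and whether study participation is the cause. The GDS and BAI scores are then used to classify events by type and by relation to the study. The same section names the serious study-related outcomes of concern, which include hospital admission for emotional causes and self-injury.

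**Between sessions.** Sections 3.3.2 and 4.1.2 encourage people to call the team with concerns. Section 5.6 adds that "participants are instructed to seek immediate medical attention for any serious adverse events that arise after the study session, rather than waiting to contact" the team.

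**Psychologist contact.** The Follow-Up Sessions paragraph of Section 3.3.2 says the psychologist risk assessment is repeated at 1 and 6 weeks, without condition. Table 2 lists risk assessment as needed. Section 4.1.2 and Appendix A tie the fuller evaluation to triggers.

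**The concern.** Psychological reaction to disclosure is a primary Stage II outcome, and the pilot is meant to say something about how people cope with the results. The scheduled instruments are symptom scales with short recall, and 35 days separate the last two contacts. As described, neither the GDS-15 nor the BAI records whether a person went to hospital, started treatment or harmed themselves.

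Suppose someone has an acute episode in week 3, receives outside care and recovers. Their week-6 scores could be normal. Because Section 4.3 classifies events through those scores, the episode may not enter the adverse-event record, and the Safety Officer, who reviews reported events, would not see it. With 10 participants receiving disclosure, one such case is 1/10 = 10% of them.

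**Working it through.** The plan gives no coverage figure, so there is nothing to reproduce. The check is a day count.

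**Inputs**
- Contacts at days 0, 7 and 42 (Sections 2.3 and 4.1.2). No visit windows are given, so nominal days are assumed.
- Look-back L: 14 days for the GDS-15 and 7 days for the BAI (Section 3.3.2).
- IES look-back: not stated. Assumed range: 7 days up to the whole time since disclosure (42 days).

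**Formula.** For each contact on day v, take the window from v − L to v and cut it to days 0 to 42. Covered days are the union of these windows, and the uncovered share is (42 − covered)/42. The day-0 contact looks back before disclosure, so it adds nothing.

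| Scale | Week-1 window | Week-6 window | Covered | Uncovered |
|---|---|---|---|---|
| GDS-15 (L = 14) | days 0–7 | days 28–42 | 7 + 14 = 21 | 21/42 = 50.0% (days 7–28) |
| BAI (L = 7) | days 0–7 | days 35–42 | 7 + 7 = 14 | 28/42 = 66.7% (days 7–35) |
| GDS-15 or BAI | days 0–7 | days 28–42 | 21 | 21/42 = 50.0% (days 7–28) |
| IES, if L = 7 | days 0–7 | days 35–42 | 14 | 28/42 = 66.7% |
| IES, if since disclosure | days 0–7 | days 0–42 | 42 | 0/42 = 0% |

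The BAI windows lie inside the GDS-15 windows, so combining the two gives the GDS-15 result.

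**With an interval question** at weeks 1 and 6 covering everything since the last contact: 7 + 35 = 42 of 42 days, so 0% is uncovered and no visit is added.

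**The risk-assessment passages side by side**
- Section 3.3.2, step 4 of the disclosure session: both dyad members have a brief assessment with a psychologist, described as drawing on the recall and impact-scale documents.
- Section 3.3.2, Follow-Up Sessions: repeated at 1 and 6 weeks, with no condition.
- Table 2, item 8: as needed.
- Section 4.1.2: a more advanced evaluation after raised GDS-15 or BAI scores, an IES score of 24 or more, or another sign of new or worse mood symptoms.
- Appendix A: a full history after listed triggers, one of which is informant concern. It covers current and past suicidal thoughts, plans, acts and psychiatric treatment, with no time limit.

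If everyone receives the Appendix A history at both follow-ups, self-harm and psychiatric treatment in the gap would probably come to light. If there are two tiers, a brief assessment for all and the full history only on a trigger, an event that has settled need not meet a trigger. The text allows either reading.

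**The case against.** The strongest reply is that the plan has several detection routes besides the two scales. The IES is anchored to disclosure and may cover the whole period. A psychologist assessment is stated to recur at both follow-ups. Informant concern is a trigger, and co-participants must be in at least weekly contact with the participant. People are encouraged to call. The exploratory satisfaction questions include an open one on overall impact. This is also a pilot with descriptive analysis only, in people screened negative for depression and anxiety.

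Much of that stands, and it limits the conclusion to events that may be missed. It does not close the gap. The IES is used as a distress score; nothing says it records admissions, self-harm or treatment. Calls and informant concerns depend on someone volunteering them, and some participants have MCI. Under Outcome 2.3 the satisfaction answers are read for suggestions and themes and are not handled as event data.

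A reader might infer more than the documents support, in four ways:
- *That most of the six weeks is unobserved.* Only the BAI leaves more than half uncovered. The GDS-15, alone or with the BAI, leaves exactly half, and the other routes mean the period is not unobserved.
- *That the 35-day gap breaks the expedited reporting limits.* It does not. Those limits start when the PI learns of an event, as in "within 48 hours of study PI knowledge of the event", and the 24-hour limit applies only to life-threatening or fatal study-related events.
- *That the Section 5.6 instruction is the defect.* It tells people not to delay care and does not discourage telling the study.
- *That nobody is asked to inform the team after seeking care.* Section 5.6 refers to the consent form, whose pages are not in the public copy, so this cannot be judged.

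**Conclusion.** The point holds as a gap in how Stage II events are ascertained. Days 7 to 28 after disclosure (21 of 42, 50%) lie outside both GDS-15 and BAI recall, and days 7 to 35 (28 of 42, 67%) lie outside BAI recall. For the IES the uncovered share runs from 0% to 67%, depending on a recall period the protocol does not state. No section schedules a question about hospitalization, self-harm or mental-health care since the last contact. An interval event that has settled by week 6 may therefore be missed unless it is volunteered or emerges in the psychologist contact.

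The percentages assume visits on nominal days 7 and 42, and they describe recall coverage, not the chance that an event is missed. How much the psychologist contact helps depends on passages that conflict. This is an inexpensive improvement to the safety data and does not undermine the design.

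**What to change.** 1. At the existing 1- and 6-week sessions, ask each dyad member separately a fixed yes/no set covering the whole time since the last contact: hospital or emergency visit for emotional reasons; self-harm thoughts or acts; new or changed mental-health treatment; any other harm the person links to the results.
2. State in Section 4.3 that these answers are adverse-event data, so that an event counts even when that day's GDS-15 and BAI scores are normal. Report them by visit alongside Outcome 2.2.
3. Reconcile Section 3.3.2 (step 4 and Follow-Up Sessions), Table 2, Section 4.1.2 and Appendix A on who receives the risk assessment at each session and what it contains. Which rule applies is for the study team to decide.
4. State the IES recall period.

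The Section 5.6 instruction to seek care stays unchanged.

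**Cost.** One form and a few protocol sentences. At an estimated two minutes per session, 2 minutes × 2 sessions × 20 people = 80 minutes over the whole pilot. The event count may look slightly less favourable.
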